PASS INFORMATIONENCEPP/SDPP/6083

Observational Study Protocol 31-13-300

Please note parts of the protocol including annexes have been currently redacted to avoid any bias to the study. The full protocol and annexes will be available when the study concludes.

Title	ABILIFY® for the Adolescent Bipolar I Mania
	Indication Tool Effectiveness Evaluation Survey
Protocol version identifier	Draft 5.0
Date of last version of protocol	15 October 2013
EU PAS register number	Study not registered
Active substance	Aripiprazole
	Antipsychotics
	ATC code: NO5AX12
Medicinal product	ABILIFY®
Product reference	PRD640634
	PRD640635
	PRD640636
	PRD640637
	PRD640638
	PRD640639
	PRD640640
	PRD640641
	PRD640642
	PRD640643
	PRD640644
	PRD640645
	PRD640646
	PRD640647
	PRD640665
	PRD640648
	PRD640649
	PRD640650
	PRD640651
	PRD640652
	PRD640653
	PRD640654

	DDDC40655	
	PRD640655	
	PRD640656	
	PRD640657	
	PRD640658	
	PRD28189	
	PRD640659	
	PRD640660	
	PRD640661	
	PRD640662	
	PRD640663	
	PRD640664	
Procedure number	EMEA/H/C/000471	
Marketing authorisation holder(s)	Otsuka Pharmaceutical Europe Ltd.	
Joint PASS	No	
Research question and objectives	The key research questions are:	
	1. What is the distribution of education material	
	across the markets?	
	2. What is the usage of the RM tools by HCPs	
	and patients / caregivers?	
	3. Do HCPs and patients / caregivers understand:	
	a. the information presented in the RM	
	tools, including	
	b. the indicated age range,	
	c. indicated dose,	
	d. duration of treatment before	
	prescribing ABILIFY	
	e. the identified and potential risks of	
	concern (extrapyramidal symptoms	
	(EPS), weight gain, somnolence,	
	fatigue) associated with ABILIFY for	
	adolescent bipolar I mania indication	
	4. Do HCPs and patients / caregivers respond	
	appropriately to hypothetical risk scenario	
	based questions regarding the clinical use of	
	ABILIFY for the adolescent bipolar I mania	
	indication, the identified and potential risks,	
	and the real-world usage, specifically the	

	recommended starting dosage, and minimum
	recommended age of patients
	The primary objectives of the study are to:
	1. To determine the proportion of HCPs, patients
	and caregivers that are aware of the RM tools
	and how the tools are accessed.
	2. To determine when, how and by whom the
	tools are used.
	3. To determine the level of knowledge and
	comprehension of the key risks associated with
	ABILIFY® when used for the treatment of
	paediatric bipolar I mania.
	4. To evaluate HCP, patient and caregiver
	behaviours via behavioural questions and
	scenarios.
	5. To assess the effect of the tools on the real-
	world risks that the educational tools have
	been designed to minimise, namely the
	maximum starting dose of ABILIFY® for the
	adolescent bipolar I mania indication is not
	exceeded, and the minimum age of patients
	receiving ABILIFY® for the adolescent bipolar
	I mania indication is not breached.
	This will be achieved by including in the HCP
	questionnaire the usual starting dose of
	ABILIFY® used in the adolescent indication,
	identifying the appropriate dose and the
	minimum age of the patient when the drug is
	prescribed, as well as the actual ages of
	patients doing the patient/carer questionnaire
Countries of study	UK, Germany, Spain, Italy, Sweden, Denmark,
	Norway, Ireland, Austria, Portugal, Slovenia,
	Greece/Cyprus
Author	[name], MD
	Acting VP Medical Affairs and Compliance - Europe
	Otsuka Pharmaceutical Europe Ltd.

ABILIFY®

[name],
[name]
United Kingdom

[contact]
Mob: [name]
[contact]

This document is the confidential and proprietary information of Otsuka Pharmaceutical Europe Ltd. and its global affiliates. By reviewing this document, you agree to keep it confidential and to use and disclose it solely for the purpose of assessing whether your organisation will participate in and/or the performance of the proposed Otsuka-sponsored study. Any permitted disclosures will be made only on a confidential "need to know" basis within your organisation or to your independent ethics committee(s). Any other use, copying, disclosure or dissemination of this information is strictly prohibited unless expressly authorised in writing by Otsuka. Any supplemental information (e.g., amendments) that may be added to this document is also confidential and proprietary to Otsuka and must be kept in confidence in the same manner as the contents of this document. Any person who receives this document without due authorisation from Otsuka is requested to return it to Otsuka or promptly destroy it. All other rights reserved.

TABLE OF CONTENTS

TABLE	OF CONTENTS	5
1	LIST OF ABBREVIATIONS	8
2	RESPONSIBLE PARTIES	9
3	ABSTRACT	10
3.1	Title	10
3.2	Rationale and Background	10
3.3	Research Question and Objectives	11
3.3.1	Research Question	11
3.3.2	Objectives	11
3.4	Study Design	12
3.5	Population	12
3.6	Variables	12
3.7	Data Sources	12
3.8	Study Size	13

1 LIST OF ABBREVIATIONS

Term	Definition
ADR	Adverse Drug Reaction
AE	Adverse Event
BMS	Bristol Myers Squibb
CI	Confidence Interval
EPS	Extrapyramidal Symptoms
EU PAS Register	European Union Post Authorisation Study Register
EU-RMP	European Risk Management Plan
НСР	Healthcare Provider
HCP FAQ	Healthcare Provider Frequently Asked Questions (one of the RM tools)
MAH	Market Authorisation Holder
PCIB	Patient Caregiver Information Brochure (one of the RM tools)
PW	Pope Woodhead – external consultants conducting the study
RM	Risk Minimisation
RMP	Risk Management Plan
SmPC	Summary of medicinal Product Characteristics
URL	Uniform Resource Locator

3.2 Rationale and Background

ABILIFY[®] (aripiprazole) is a drug indicated for the treatment up to 12 weeks of moderate to severe manic episodes in Bipolar I Disorder in adolescents aged 13 years and older. It was approved by the European Commission on January 24th 2013. For reasons of conciseness, the indication throughout this protocol is termed **adolescent bipolar I mania**.

As part of marketing authorisation approval, the ABILIFY® risk management plan (RMP) requires distribution of two Risk Minimisation (RM) communication tools, additional to the SmPC, to Healthcare Providers (HCPs) prescribing ABILIFY® for the adolescent bipolar I mania indication. This distribution is managed by BMS / Otsuka or Lundbeck depending on the timeline and status for local transfer of responsibility in each country.

These tools are a Healthcare Provider Frequently Asked Questions Brochure (HCP FAQ) and a Patient / Caregiver Information Brochure (PCIB). The purpose of the HCP FAQ is to clearly explain to prescribers or other HCPs involved in patient treatment the need to carefully consider the indicated age range, dose, and duration of treatment before prescribing ABILIFY[®] for the adolescent bipolar I mania indication. Furthermore, vigilance is urged in the on-going evaluation of weight gain, EPS, and ADRs related to somnolence and fatigue. A PCIB is available for physicians to give to their patients (and their caregivers) to help them better understand and recognise specific ADRs.

The EU-RMP committed Otsuka Pharmaceutical Europe Ltd., as the marketing authorisation holder (MAH), to evaluate the effectiveness of these additional RM activities (i.e. the RM tools and their distribution) for the adolescent bipolar I mania indication. This protocol describes the method for the HCP and Patient / Caregiver surveys that will be used to evaluate the

effectiveness of these RM tools, defined as a combination of effective distribution, usage, knowledge and adoption of appropriate stakeholder behaviours.

It should be noted that, for the duration of the surveys described in this protocol, Bristol-Myers Squibb (BMS) will retain responsibility for pharmacovigilance until Otsuka takes over responsibility for pharmacovigilance for ABILIFY[®] (mid 2016). Otsuka (the MAH) and Lundbeck affiliates (alliance partners in some markets participating in the survey) will be responsible for the operational aspects of implementing the surveys.

The results of the surveys are intended to assess the value of the current RM tools and to establish baseline levels of usage, knowledge and behaviours. The results will be reported to the EMA, and, if appropriate, lead to the modification of the ABILIFY[®] EU-RMP for the adolescent bipolar I mania indication. In addition, the results of the evaluation will inform the need for, and timing of, any subsequent tool evaluations.

3.3 Research Question and Objectives

3.3.1 Research Question

The key research questions are as follows:

- 1. What is the distribution of educational material across the markets?
- 2. What is the usage of the RM tools by HCPs and patients / caregivers?
- 3. Do HCPs and patients / caregivers understand:
 - a. The information presented in the RM tools, including:
 - i. the indicated age range,
 - ii. indicated dose,
 - b. Duration of treatment before prescribing ABILIFY[®], and
 - c. The identified and potential risks of concern (extrapyramidal symptoms (EPS), weight gain, somnolence, fatigue) associated with ABILIFY® for adolescent bipolar I mania indication?
- 4. Do HCPs and patients / caregivers respond appropriately to hypothetical risk scenario-based questions regarding the clinical use of ABILIFY[®] for the adolescent bipolar I mania indication, the identified and potential risks, and the real-world usage specifically the recommended starting dosage, and minimum recommended age of patients?

3.3.2 Objectives

The objectives of the study are to evaluate the effectiveness of educational RM tools for ABILIFY® used in the adolescent bipolar I mania indication, in markets where this indication has been approved and ABILIFY® subsequently prescribed for at least six months.

The primary objectives of the study are:

1. To determine the proportion of HCPs, patients and caregivers that are aware of the RM tools and how these tools are accessed

- 2. To determine when, how and by whom the tools are used
- 3. To determine the level of knowledge and comprehension of the key risks associated with ABILIFY[®], when used for the treatment of paediatric bipolar I mania
- 4. To evaluate HCP, patient and caregiver behaviours using behavioural questions and scenarios and minimisation of inappropriate starting dose and patient age

The evaluation is planned to be performed 12 months after implementation of the educational measures in up to 13 EU member states (where use of aripiprazole in paediatric patients is possible due to the availability of the oral solution, used at treatment initiation) to allow sufficient time for use and experience of the RM materials to conduct a meaningful assessment.

3.4 Study Design

This is a non-interventional, observational, cross-sectional study using HCP, Patient and Caregiver surveys. The surveys are intended to evaluate participants' awareness and use of tools, their knowledge of ADRs of interest, and their behaviours when presented with hypothetical risk scenarios. The surveys themselves are not intended as a mechanism for collecting ADR reports.

3.5 Population

The study population will comprise the target audiences for the RM tools (HCPs, and Patients and Caregivers) in markets where ABILIFY[®] has been used for the adolescent bipolar I mania indication for more than six months.

3.6 Variables

Variables of particular interest include:

- Patient age
- ABILIFY® dose
- Treatment duration
- Number of previous treatments
- HCPs' experience using ABILIFY® for the adolescent bipolar I mania indication
- Tool usage
- Medical speciality
- Geographical location (country)

3.7 Data Sources

The survey will include web-based structured questionnaires mainly comprising multiple choice questions, in addition to scenarios and some descriptive comments sections.

Protocol Number: 31-13-300 ABILIFY[®]

3.8 Study Size

Sample size is based upon an acceptable margin of error defined as less than 20% in the population of interest, with a significance level of < 0.05, and a correct response distribution to a knowledge-based question of 85%. This is anticipated to yield between 148 and 158 HCPs, and 148 to 158 patients participating, once the final evaluation has been completed.

3.9 Data Analysis

Descriptive statistics for discontinuous data will be used to examine the key research questions of interest. The data for the overall population will be examined by users and non-users, general psychiatrists, child / adolescent psychiatrists, nurses, pharmacists, patients and caregivers, and individual countries. The data will be presented with responses' frequency distributions and 95% confidence intervals.

3.10 Milestones

The study is planned to start 12 months following the launch of ABILIFY® for the adolescent bipolar I mania indication in each market. It is assumed that CHMP approval of the protocol will have been obtained by this time.

The protocol will, thereafter, be registered on the EU PAS Register (currently the E-Register of Studies) within one month of CHMP / PRAC approval (Q1 2014).

The content of the surveys will be finalised in Q1 2014, around a month later.

Study recruitment will start in Q2 2014, with data collection commencing around 2 months later, in Q2/3 2014.

Data collection is expected to take around 6 months to complete. The end of data collection, therefore, is expected to be in Q4 2014.

Analysis and reporting of results will be complete within four months of the end of data collection, between Q4 2014 and Q1 2015.

Protocol Number: 31-13-300 ABILIFY®

4 AMENDMENTS AND UPDATES

This is the second draft of the protocol, which addresses the feedback from the CHMP conclusion on 19 September 2013.

Protocol Number: 31-13-300 ABILIFY®

5 MILESTONES

The key milestones for this study are shown in Table 6-1:

Table 6-1: Study Milestones

Milestone	Planned Date
Registration in the EU PAS register	Q1 2014
Survey content finalisation	Q1 2014
Recruitment starts	Q2 2014
Start of data collection	Q2/3 2014
End of data collection	Q4 2014
Study progress report	Not planned
Interim report	Not planned
Final report of study results	Q4 2014 to Q1 2015

6 RATIONALE AND BACKGROUND

Bipolar I disorder (formerly called manic depression) in paediatrics is characterised by the occurrence of one or more manic or mixed (manic-depressive) episodes. It can significantly impact the wellbeing of the paediatric patient, and can negatively impact relationships with friends and family or success at school.

ABILIFY® (aripiprazole) is a drug indicated for the treatment up to 12 weeks of moderate to severe manic episodes in Bipolar I Disorder in adolescents aged 13 years and older. It was approved by the European Commission on 24 January 2013. For reasons of conciseness the indication throughout this protocol is termed **adolescent bipolar I mania**.

The early diagnosis and prompt management of Adverse Drug Reactions (ADRs), according to recommended guidelines, is important for minimising the potential of severe outcomes. As part of marketing authorisation approval, Otsuka has implemented a risk management plan (RMP) that distributes two RM communication tools, additional to the SmPC, to HCPs prescribing ABILIFY® for the adolescent bipolar I mania indication.

Specifically, the two RM tools, additional to the SmPC, from the EU-RMP are:

1. Healthcare Professional Frequently Asked Questions (FAQs) Brochure

A reference document in a Q&A format which informs HCPs about administering ABILIFY® for the adolescent bipolar I mania indication, and appropriately identifying and managing ADRs. The brochure also guides HCPs on distributing the Patient / Caregiver information brochure, educating patients / caregivers about ADRs and the need to contact the treating physician if signs of ADRs are suspected.

The purpose of the FAQs Brochure is to clearly explain to prescribers the need to carefully consider the indicated age range, dose, and duration of treatment before prescribing ABILIFY[®] for the indication of adolescent bipolar I mania.

Furthermore, vigilance is urged in the on-going evaluation of weight gain, EPS, and ADRs related to somnolence and fatigue.

Overall, the HCP Brochure is designed to inform HCPs about ABILIFY® treatment in this indication, highlight ADRs of concern, remind them to discuss potential ADRs, and to distribute tools to patients / carers. This education is aimed at raising awareness and vigilance in the HCP and patient populations.

2. Patient / Caregiver Information Brochure (PCIB)

A reference document provided to HCPs for distribution to their patients / caregivers outlining the treatment of adolescent bipolar I mania with ABILIFY, including advice on being vigilant for adverse drug reactions (ADRs) and contacting their treating physician immediately if signs of ADRs are suspected. Overall, the Patient brochure is designed to educate patients and carers on how to take ABILIFY®, to be vigilant for ADRs and report

immediately.

The key risks minimised by these RM tools are:

- Weight gain
- Extrapyramidal symptoms (EPS)
- Fatigue, and
- Somnolence

Another critical aspect of the risk minimisation education is to ensure that that maximum recommended dose is not exceeded and the minimum age of patients is not breached and the effectiveness evaluation survey will collect specific data to evaluate knowledge and prescribing behaviours for age and dose.

The tools clearly state the importance of being vigilant for the ADRs of concern and reporting them immediately, should they arise.

The RM tools also cover the contraindications and other common side-effects that are described in the product labelling. Further to this, the tools discuss how treatment should be initiated and titrated, that the treatment regimen should only be altered, or discontinued, by the prescriber. The EU-RMP committed Otsuka Pharmaceutical Europe Ltd., as the marketing authorisation holder (MAH), to evaluate the effectiveness of these additional RM activities for the adolescent bipolar I mania indication. This protocol describes the method for the HCP and Patient / Caregiver surveys that will be used to evaluate the effectiveness of these RM tools defined as a combination of effective distribution, usage, knowledge and adoption of appropriate stakeholder behaviours.

It should be noted that, for the duration of the surveys described in this protocol, Bristol-Myers Squibb (BMS) will retain responsibility for pharmacovigilance until Otsuka takes over responsibility for pharmacovigilance for ABILIFY[®] (mid 2016). Otsuka (the MAH) and Lundbeck affiliates (alliance partners in some markets participating in the survey) will be responsible for the operational aspects of implementing the surveys.

The results of the surveys are intended to assess the value of the current RM tools (additional to the SmPC) and to establish baseline levels of usage, knowledge and behaviours. The results will be reported to the EMA and, if appropriate, lead to the modification of the ABILIFY® EU-RMP for the adolescent bipolar I mania indication. In addition, the results of the evaluation will inform the need for, and timing of, any subsequent tool evaluations.

Protocol Number: 31-13-300 ABILIFY®

7 RESEARCH QUESTION AND OBJECTIVES

7.1 Research Question

The key research questions are as follows:

- 1. What is the distribution of educational material across the markets?
- 2. What is the usage of the RM tools by HCPs and patients / caregivers?
- 3. Do HCPs and patients / caregivers understand:
 - a. The information presented in the RM tools, including:
 - i. the indicated age range,
 - ii. indicated dose,
 - b. The appropriate duration of treatment before prescribing ABILIFY, and
 - c. The identified and potential risks of concern (extrapyramidal symptoms (EPS), weight gain, somnolence, fatigue) associated with ABILIFY® for adolescent bipolar I mania indication?
- 4. Do HCPs and patients / caregivers respond appropriately to hypothetical risk scenario-based questions regarding the clinical use of ABILIFY® for the adolescent bipolar I mania indication, the identified and potential risks, and the real-world usage specifically, the recommended starting dosage and minimum recommended age of patients?

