- 1. To determine the proportion of HCPs, patients and caregivers that are aware of the existence of the RM communication tools and how these tools were accessed (i.e. paper or electronic versions).
- 2. To determine who uses the RM communication tools, and how, when and how often they are used.
- 3. To determine the level of knowledge and comprehension of the key elements of identified risks of concern associated with ABILIFY® for the adolescent bipolar I mania indication (i.e. EPS, weight gain, somnolence and fatigue).
- 4. To assess the effect of the tools on the real-world risks that the educational tools have been designed to minimise, namely the maximum starting dose of ABILIFY® for the adolescent bipolar I mania indication is not exceeded, and the minimum age of patients receiving ABILIFY® for the adolescent bipolar I mania indication is not breached.
- 5. To evaluate the HCP, patient and caregiver behaviours via behavioural questions and scenarios.

The following tables illustrate which components of the surveys will be used to carry out these evaluations:

Table 1: Demographic questions

Annex	Questions examining participant demographics
Annex 1: HCP survey	1 to 4
Annex 2: Patient survey	1 to 3
Annex 3: Caregiver survey	1 to 3

Table 2: Understanding RM tool awareness and distribution

Annex	Questions designed to understand RM tool awareness
	and distribution
Annex 1: HCP survey	7, 8, 15, 16
Annex 2: Patient survey	4, 5
Annex 3: Caregiver survey	4, 5

ABILIFY®

Table 3: Understanding RM tool use and utility

Annex	Questions designed to understand tool use and	
	utility	
Annex 1: HCP survey	9 to 14, and 17 to 23	
Annex 2: Patient survey	6 to 11	
Annex 3: Caregiver survey	6 to 13	

For this survey, the intention is to primarily test knowledge indirectly, as meeting behavioural goals will require some degree of working-knowledge of ABILIFY[®] benefits and risk, when used for the adolescent bipolar I mania indication.

Tables 4 and 5 contain the questions that reflect understanding of how to take ABILIFY[®], how to treat ADRs (HCPs), and awareness of risks and what to do if risks are identified (patients / caregivers).

Table 4: Understanding knowledge of RM tool content

Annex	Questions designed to understand knowledge of tool	
	content	
Annex 1: HCP survey	24 – 35	
Annex 2: Patient survey	12 – 33	
Annex 3: Caregiver survey	14 – 35	

Table 5: Knowledge of potential or identified risks of concern

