Identified or potential	Question item in	Question item in Patient /
risk of concern	HCP survey	Caregiver survey
Age range	4	(Note that age of patients will be
		collected as a demographic (Q2).
		This may indirectly help to
		understand if ABILIFY® is
		prescribed to appropriate patients
		in this indication.)
Dose	5	Indirectly 12 -17 (Patients), 14-19
	Case Studies 1 (24) 2	(Caregivers)
	(25) and 3 (28)	
Duration of treatment	Case studies 3 (29)	Indirectly 3
	and 4 (31-33)	
Extrapyramidal symptoms	30	24 – 26 / 26 – 28
(EPS)		

Weight gain	26, 34, 35	19 – 23 / 21 – 25
Somnolence	32	30 – 32 / 32 – 34
Fatigue	31, 33	27 – 29 / 29 – 31

Table 6: Understanding behaviours

Appendix	Questions designed to understand behaviours
Appendix 1: HCP survey	Case studies
Appendix 2: Patient survey	23, 26, 29, 32
Appendix 3: Caregiver survey	25, 28, 31, 34

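### Research question 4 asks for scenario responses on the minimum patient age, but the protocol's item map assigns no scenario item to age in any of the three surveys

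*Protocol*

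**What the plan says.** Research question 4 in section 7.1, repeated in section 3.3.1 and the opening synopsis, begins "Do HCPs and patients / caregivers respond appropriately to hypothetical risk scenario-based questions regarding the clinical use of ABILIFY". It closes by naming the topics covered: "specifically, the recommended starting dosage and minimum recommended age of patients". Both HCPs and patients / caregivers are its subjects. Research question 3 asks whether the same groups understand the indicated age range.

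Section 6 treats the dose and age limits as a critical part of the education. It commits to ensuring that "the minimum age of patients is not breached and the effectiveness evaluation survey will collect specific data to evaluate knowledge and prescribing behaviours" for both.

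Section 8.1 then allots questionnaire items to topics:

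- Table 1, headed "Questions examining participant demographics", has the entry "Annex 1: HCP survey 1 to 4".
- Table 4 gives the knowledge-of-content blocks: HCP 24-35, patient 12-33, caregiver 14-35.
- Table 5 gives HCP Q4 for age. For dose it gives Q5 and then "Case Studies 1 (24) 2" (25) and 3 (28). In the patient / caregiver column the age row has only a remark beginning "Note that age of patients will be", which goes on to say that Q2 is a demographic item of possible indirect use.
- Table 6, on behaviours, has the entry "Appendix 1: HCP survey Case studies".

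Table 7 in section 8.3 marks recommended age as an HCP metric and as N/A for patients / caregivers.

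**The concern.** Section 8.1 says that knowledge is to be tested mainly indirectly, through behaviour, and Table 6 places HCP behaviour in the case studies. Section 8.6 counts the measurement of behavioural choice among its safeguards against socially desirable answers. Scenarios are thus the main instrument, and research question 4 relies on them for both prescribing limits.

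Dose has a direct question and three case-study items. Age has a direct question and no mapped case study. Run on this map, the survey would report scenario performance to the EMA with no result identified as bearing on age, although the research question announces one. It would also have no measure of whether patients and caregivers understand the age range, which research question 3 promises and Table 7 excludes.

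**Working it through.** The point depends on no sample size, power or error rate, and the protocol states no figure for it. The check compares the item numbers in Tables 1 and 4 to 7.

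**Step 1. HCP survey.** The Table 4 block 24-35 has 35 - 24 + 1 = 12 items. Table 5 assigns them as follows (some appear twice):

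| Topic | HCP items inside 24-35 | HCP items outside |
|---|---|---|
| Age | none | 4 |
| Dose | 24, 25, 28 | 5 |
| Duration | 29, 31, 32, 33 | none |
| EPS | 30 | none |
| Weight gain | 26, 34, 35 | none |
| Somnolence | 32 | none |
| Fatigue | 31, 33 | none |

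The distinct mapped items are 24, 25, 26 and 28 to 35, which makes 11. Item 27 has no topic. Age: 0 of 11. Dose: 3 of 11.

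Table 5 names case studies where they apply: 1, 2 and 3 for dose, 3 and 4 for duration. It names none for age. The single age item, Q4, falls within Table 1's demographic range 1 to 4.

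**Step 2. Patient survey.** The block 12-33 has 22 items. Table 5 maps 12-17 (6, dose, indirectly), 19-23 (5, weight gain), 24-26 (3, EPS), 27-29 (3, fatigue) and 30-32 (3, somnolence). The sum is 6 + 5 + 3 + 3 + 3 = 20. Items 18 and 33 have no topic. Age: 0 of 20.

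**Step 3. Caregiver survey.** The block 14-35 has 22 items. Table 5 maps 14-19 (6), 21-25 (5), 26-28 (3), 29-31 (3) and 32-34 (3), again 20. Items 20 and 35 have no topic. Age: 0 of 20.

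**Step 4. Behaviour items.** Table 6 lists patient items 23, 26, 29 and 32 and caregiver items 25, 28, 31 and 34. In order, these fall in the weight gain, EPS, fatigue and somnolence ranges above. None concerns age.

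**Step 5. Who is asked about age.** Research questions 3 and 4 include patients / caregivers. Objective 3a in section 7.2.1 restricts dosage to HCPs but, on its natural reading, not age range. Table 7 gives N/A for patients / caregivers on age. These statements do not agree. Section 8.2.2 says that Q2 asks the patient's age when treatment began. That is a fact about the patient, not a test of understanding or a response to a scenario.

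**Step 6. What the map leaves open.** Five block items have no topic: HCP 27, patient 18 and 33, caregiver 20 and 35. HCP item 6 is in none of the tables but lies outside the 24-35 block.

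**The case against.** The strongest reply is that age is assessed by another stated route. Section 7.2.1 says the HCP questionnaire will cover the minimum patient age at prescribing, and that the actual ages of surveyed patients will be used. With 148 to 158 patient / caregiver surveys planned, reported age at initiation bears on actual prescribing, which scenarios reach only indirectly (section 8.6). Section 7.2 lists scenario responses and the minimisation of inappropriate dose and age as separate aims, and the primary endpoints in section 8.1 separate them too. On this view research question 4 is one compressed sentence that runs hypothetical and real-world matters together. The section 6 commitment to collect data on age does not by itself require a scenario.

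Most of this stands. A reader might infer that age goes unmeasured, or that the age result rests on one item. The documents do not support either, because HCP Q4 and patient / caregiver Q2 both feed it. A reader might also infer that no questionnaire contains an age scenario. That cannot be said either: the annexes are withheld, and five block items have no stated topic. Nor is the double listing of Q4 proof of error, since an item may serve two tables; Table 5 itself lists 31 to 33 under more than one topic.

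The reply does not remove the mismatch. Research question 4 names age as scenario content, and no mapped scenario item carries it. If an unmapped item does test age, Table 5 is incomplete and needs the entry. The N/A in Table 7 contradicts research questions 3 and 4 whatever the annexes contain.

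**Conclusion.** The point holds in a limited form. On the protocol's own map, two things lack a measure: scenario responses on the minimum age, and patient / caregiver understanding of the age range. The real-world age objective keeps its direct HCP question and the reported ages.

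The zero counts in the working apply to mapped items only. They assume that Table 5 lists the relevant items for each topic it names, and they say nothing about the content of the five unmapped items. The protocol needs correcting because its research question promises a result that its stated instrument does not identify.

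**What to change.** Before survey content is finalised (planned for Q1 2014 in section 5), take one of two routes:

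1. Add one HCP scenario item, or identify an existing one, scored on whether the respondent recognises that the patient is outside the indicated age as the protocol states it. Map that item to age in Table 5.
2. Remove age from the scenario part of research question 4, and state that age is assessed by HCP Q4 and patient / caregiver Q2.

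Under either route, limit the age part of research questions 3 and 4 and of objective 3a to HCPs, to agree with Table 7. State in Tables 1 and 5 whether HCP Q4 is a demographic item, a knowledge item or both.

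Converting unmapped item 27 into the age item is not a safe shortcut. Table 5 places case study 2 at item 25 and case study 3 at item 28, so 27 probably shares a vignette with dose item 25 and weight-gain item 26. Changing the patient in that vignette could alter all three.

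The cost of route 1 is at most one extra HCP item, a slightly longer survey (currently about 25 minutes for HCPs) and renumbering if the item is inserted within the block. Route 2 costs wording only, but gives up scenario evidence on age. Neither needs more participants.
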